5.8.1.2 Propensity score matching

Objective:	Data Variables:	Data Source:
Construct a control group for study participants	
 • Flag of infusion treatment • Symptomatic flag • Demographic • Elixhauser conditions 	
 • Optum infusion pharmacy data • UHC claims data • CDSM • BCRT

- Optum EMR data

The objective of propensity score matching is to ensure balance between the treatment and control group on the selected covariates. Propensity score matching will be conducted after the completion of treatment enrollment (28-day study period) and upon the availability of information of study participants. Data sources of information for calculating the propensity scores for study participants will be Optum infusion pharmacy data, UHC claims data, and CDSM data. Note for the matched controls we will select them from Optum EMR+claims dataset, we will include only members who are COVID diagnosed, have documented symptoms of COVID-19, meet the inclusion/exclusion criteria for the study, and have historical information about selected risk factors (either through claims or EMR).

According to the current study eligibility criteria in Section 4.4.1, the treatment group consists of both UHC and non-UHC members. While UHC patients with continuous enrollments have pertinent historical information (i.e., comorbidity, demographic), accruing such information might be challenging and is likely unavailable for non-UHC members. We will first perform matching for the UHC-treated members with complete information. Next, we will exclude the selected matched-control individuals for each UHC-treated from the control set. The non-UHC patients will be matched sequentially case-by-base from the remaining control group for each outstanding treated participant using “exact” matching method based on available information. Note that, such exact matching for patients without relevant comorbidity variables may result in sub-optimal match.

The following description of matching methods is for UHC members in the treatment group. We will apply propensity score matching techniques described in (Guo, 2014), and fit a GLM using matching covariates as selected risk factors of COVID-19 hospitalizations from Section 5.8.1.1 and response as the log odds of receiving treatment with a logit link, and estimate balancing (i.e., propensity) scores which are next to be used in finding the matched pair between treatment and control group. Model performance will be evaluated by pseudo R-square values (e.g., McFadden) and Hosmer-Lemeshow test. We will use nearest neighbor matching with a caliper which its size will be determined empirically. Note this matching model is different from 5.8.1.1 in terms of response (hospitalization flag vs receiving treatment). We will evaluate balance in covariates between study participants and matched controls by absolute standardized difference in mean (Austin, 2009) and variance ratio of propensity score and covariates since it is more robust in terms of sample size and covariate distribution requirements in comparison to other balance diagnostics (Ali, 2016). We will also conduct a hypothesis test to examine if a significant difference in matching covariates exists between treatment and control groups, such as Wilcoxon rank-sum (Mann-Whitney) test or *t*-test for continuous variables and Chi-squared test for categorical variables. We will use these tests to evaluate covariate balances before and after matching and repeat the processes if covariate imbalances remain.

We will consider nearest neighbor matching within a caliper (Smith, 2005), and obtain 1-to-1 match. As an alternative approach, optimal matching technique may also be adopted, in the event that the covariate imbalances persist using the prior methods. In addition, greedy matching methods make decisions about inclusion of a pair of treated-control participants as a matched set sequentially; here decisions are made one at a time without reconsidering early decisions as later ones are made. From this point of view, such mechanism is not optimal and therefore optimal

Commented [XM32]: Please describe in detail on how to estimate PS. Use the variables selected from 5.3.2.1 or redo the model selection?

Commented [JAT33R32]: Variables selected from the previous section. Added this specification in the second sentence of this paragraph.

Commented [WWY34]: Suggest to be more specific for what will be test for non-parametric method

matching based sensitivity analyses will be performed to assess the numerical performances. In addition, propensity score subclassification (Rosenbaum, 1984) in conjunction with trimming strategy (Crump, 2009) will be adopted. Such greedy matching methods require a sizable (e.g., 70%) common support region for logit between treated and control, known as “overlap assumption”. It is possible that greedy matching excludes participants because treated cases fall outside the lower end of the common support region (those who have low logit) and nontreated cases fall outside the upper end of the common support region (those who have high logit). This can be investigated once we fit PSM model, estimate the logits, and plot them side-by-side for treated and control. If we see significant nonoverlap then we may need to try alternative such as trimming method.

One of the key limitations is - covariates in the propensity model may not be statistically significant resulting in suboptimal probability estimation of treatment assignments (or propensity scores).

5.8.1.3 Primary efficacy outcome analysis: COVID-related hospitalization rate at Day 28

Objective:	Data Variables:	Data Source:
Compare and determine if there is a significant difference in the rate of COVID-19 related hospitalization between study participants and matched controls	
 Flag of COVID-19 related hospitalization through Days 1-28 Flag of infusion treatment Demographics Elixhauser conditions 	
 Optum infusion pharmacy data UHC claims data CDSM COVID labs data BCRT COVID hospitalizations data Optum EMR data

Commented [XM35]: Please be specific which endpoint will be used for the primary analysis binary or time-to-event?

Commented [JAT36R35]: Specified in Section 4.5 Endpoint.

Commented [TEE37R35]: Added in parenthesis to further clarify in first sentence.

Commented [WWY38]: If add a table of Populations for Analyses, this table may not need (see attached sample SAP)

Commented [JAT39R38]: I added the table of populations for analyses in Section 5.1.1. but still want to keep the table with objective, data variables and data source here since they contain different information.

Understanding the COVID-related hospitalization rate at Day 28 (binary endpoint) between study participants and matched controls is the key primary objective. We consider the analysis in combinations of with/without time-related outcome and with/without covariate adjustment. A single model will be selected and documented prior to accessing outcome data with the focus of including covariates expected to be strongly related to outcome based on other studies.

First, consider the simplest scenario without covariates adjustment and time-related outcome; we will use nonparametric McNemar's test to compare the hospitalization rate at Day 28 between the treatment and control groups at the level 0.05. Separately, for those who are not admitted due to COVID at Day 28, we will treat their non-hospitalization as a censored response after Day 28, instead of assuming no COVID hospitalizations after Day 28. Without covariates adjustment, we will draw Kaplan-Meier curves and perform log-rank test to compare the equality of curves implying similar cumulative incidence of hospitalization between the treatment and control groups over 28-day period.

Next, consider covariates adjustment, this will allow us to compare hospitalization rate between treatment and control groups given a subset of matching covariates or covariates not included in matching. Without any covariate adjustments, treatment effect might be subject to potential confounding variables. We will construct a multiple generalized linear model with fixed or

Commented [XM40]: Please specify the link, dist

mixed effects and a logit link to examine if the hospitalization rate differs between study participants and matched controls after adjusting demographics (e.g., age, gender, etc.) and comorbidities (e.g., Elixhauser conditions). The appropriateness of using mixed model will be determined by information criteria (AIC or Bayesian information criteria (BIC)) values.

Considering the time component in the response, we will use Cox proportional hazard model, accelerated failure time model and other survival models. Proportionality assumption of the Cox model will be checked by Schoenfeld residuals. Method selection will depend on if model assumptions hold in our data.

In the short term, we will use Optum infusion pharmacy data and BCRT data to identify hospitalization among the treatment group; and we will use UHC claims data and Optum EMR data for inpatient records for identification of COVID-related hospitalizations among the control group. We will evaluate treatment effects based on a two-sided test with a level of 0.05 for all efficacy analyses, and provide 95% confidence intervals for the odds ratio/hazard ratio.

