Study participants	Optum infusion pharmacy data	Day 1 at-home infusion will collect vitals and other essential data pre, during and post-infusion using an established case report form (CRF) to collect any events experienced during and post-infusion related to Bamlanivimab (LY3819253)
	ProtectWell data	during symptom tracking – status of what was selected per daily check-in, first trigger point of noting experiencing symptoms, if COVID-19 positive and received infusion – Day 1-28 wellness tracking (in numeric 1-10 ratings)
	UHC claims data (UHC members only)	data including demographic characteristics (e.g., age, gender, race) and existing comorbidities (e.g., congestive heart failure, diabetes, chronic kidney disease)
	Blended Census Reporting Tool (BCRT) data (UHC members only)	real-time inpatient admission data including ICD-10 diagnosis codes, discharge status, COVID test status reviewed by UHC's clinical team; will be used as complementary to Optum infusion pharmacy data for COVID hospitalizations
	Clinical Data Services Management (CDSM) data (UHC members only)	SARS-CoV-2 lab testing data from reporting health systems, clinics, and third-party labs; will be used as complementary to Optum infusion pharmacy data for COVID tests
Potential pool of controls	Optum EMR data	primary source to confirm for presence of symptoms during COVID+ test of a matched individual (analogous to the symptoms collected as part of ProtectWell data for study participants); will also be used for COVID test status and COVID hospitalization of all potential controls, and for demographic characteristics, existing comorbidities, COVID test status and COVID hospitalization of potential non-UHC controls.
	UHC claims data (UHC members only)	data including demographic characteristics (e.g., age, gender, race) and existing comorbidities (e.g., congestive heart failure, diabetes, chronic kidney disease)
	Blended Census Reporting Tool (BCRT) data	real-time inpatient admission data including ICD-10 diagnosis codes, discharge status, COVID test

LY3819253

(UHC members only)	status reviewed by UHC's clinical team; this dataset does not include symptom information during COVID test, hence it will be only used as a potential sensitivity analysis data source

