4.4.2 Patient Groups

Before analysis there are two study populations – study participants and the pool of potential controls. For study participants, we plan to enroll aged 65 and older, who are deemed high risk per the emergency use authorization, if contracting COVID-19. For the pool of potential controls, we plan to utilize UHC members who have Optum EMR data to confirm presence of symptoms during COVID test as well as having continuous enrollment to access to their claims and prospective hospitalization and death data. If applicable, non-UHC members or UHC members who did not seek care at OptumCare facilities may be used as members of the control population based on EMR review and matching to enrolled participants.

During analysis (i.e., after matching), there will be two study populations – study participants after matching and matched controls. Note that the size of study participants after matching may be smaller than the size of original study participants if a matched control can't be identified.

The targeted number of enrolled participants for tracking for symptoms is 500,000, and the targeted number of study participants who are COVID-19 positive and consent to receive Bamlanivimab (LY3819253) is 7,500. Figure 2 illustrates the process to identify study participants. Regarding controls, we set the case:control ratio at 1:1 and plan to identify 7,500 matched controls which is the same as number targeted for study participants.

Given the current enrollment speed (as of March 9, 2021) and the decreasing COVID-19 hospitalization rate across the US, we may not achieve the target number of study participants, 7,500. However, according to the power analysis in Section 4.3, it is sufficient to have 1,000 study participants with another 1,000 matched controls to detect a 33% decrease in the hospitalization rate (i.e., from 15% to 10%) with power 0.8 and level 0.05.

Commented [JAT7]: Remove as treatment is allowed in this situation per the EUA.

Commented [JAT8]: Remove prior vaccination from exclusion criteria as this is not required per the EUA.

Commented [WWY9]: Should we replace continuous member enrollment?

Commented [WWY10]: Given current enrollment speed, it will be helpful to show what is the minimal sample size for Bam treated group required for the primary objective analysis.

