Commented [JAT20R19]: Agreed. We include obesity as a comorbidity in 4. Comorbidities in 2019 part below. This comorbidity is extracted from our claims data.

It makes perfect sense to include BMI, but we don't have this numerical value from the claims data and have very limited coverage from other data sources.

3. Insurance:

Variable	Data source for study participants	Data source for matched controls
Line of business		
Dual-eligibility status		
Continuous member enrollment in 2019	UHC claims	Optum EMR or UHC claims
Continuous member enrollment in 2020		
Continuous member enrollment in 2021 (up to available months)		

4. Comorbidities in 2019:

Variable	Data source for study participants	Data source for matched controls
Elixhauser score for readmission	UHC claims	Optum EMR or UHC claims
Historical flag for all associated comorbidities used in computing Elixhauser score*		

*: The 29 categories include diabetes, obesity, chronic pulmonary disease, congestive heart failure, etc. The full list is in Table A2 of Appendix 1.

Commented [WWY21]: Will comorbidities be looking only in 2019?

Commented [JAT22R21]: Yes, we chose the year 2019 because the year 2020 is a special year, and people tend to use healthcare less than usual. Besides, we assume that comorbidities listed here last to the end of our study or even longer given most of them are chronic (e.g. T2D, renal failure, congestive heart failure) and our study cohort is the Medicare Advantage cohort.

5. Immunosuppressive treatment

Variable	Data source for study participants	Data source for matched controls
History of receiving immunosuppressive treatment 6 months prior to date of COVID diagnosis*	UHC claims	Optum EMR or UHC claims

*: Please see the full list of immunosuppressive prescriptions in Table A3 of Appendix 1.

Phase II.A: Post COVID-19 diagnosis data: Study participants and Matched controls

Variable	Data source for study participants	Data source for matched controls
Date of COVID-19 admission (if hospitalized)		

CONFIDENTIAL

[Protocol number: UHG (J2X-NS-I002)] SAP [\[v.3\]](#)

ER flag (admitted from ER; if data is available)		
ICU flag (related to ICU transfer; if data is available)	BCRT	Optum EMR or BCRT
Ventilation flag (use of ventilation; if data is available)		
Diagnosis code – primary		
Diagnosis code – secondary		
Diagnosis code – tertiary		
Date of discharge (if applicable)		
Date of death (if applicable)		

Phase II.B: Post COVID-19 diagnosis data: Study participants only

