5.1.1 Populations for Analyses

We define the analysis populations in Table 3 along with the analysis we will conduct. All patients meet the study eligibility criteria. Note that all populations for analyses are UHC members, and the following proposed analytical methods are for UHC members. We may see non-UHC members satisfying the study eligibility criteria, but we cannot obtain or have very limited information of their comorbidities, demographic (e.g., area of residence, socioeconomic index), and if having immunosuppressive treatment prior to COVID-19 diagnosis.

Table 3. Population for analyses

Population	Data for analysis	Definition/Data
Study participants	Disposition analysis and safety	Study participants who sign informed consent and receive Bamlanivimab in single infusion of 700 mg.
Pool of potential controls	Formation of the control group Pre-matching identification of risk factors Estimation of prognostic scores	Patients who meet the study eligibility criteria but did not receive Bamlanivimab.

Commented [WWY23]: Would suggest to revise to include general results reporting, definition of the analysis populations, analysis methods, definition of baseline Refer to attached sample SAP

Overall population	Descriptive analyses Propensity score matching	Consists of study participants and pool of potential controls.
Propensity score matched population	Efficacy and descriptive analyses	Subset of the overall population consisting of study participants and matched controls after propensity matching.
Double score (propensity score and prognostic score) matched population	Sensitivity analyses	Subset of the overall population consisting of study participants and matched controls after double matching.

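### The SAP lets comorbidity and immunosuppressant matching covariates come from different sources in the two groups, and contradicts itself on whether controls with EMR-only history enter the primary match

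*SAP*

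**What the plan says.** **Participants.** SAP 5.8.1.2 states: "Data sources of information for calculating the propensity scores for study participants will be Optum infusion pharmacy data, UHC claims data, and CDSM data". EMR is not among them. The comorbidity and immunosuppressant rows of SAP 4.7 give UHC claims alone.

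**Controls.** The same rows of SAP 4.7 give "Optum EMR or UHC claims". SAP 5.8.1.2 admits controls who "have historical information about selected risk factors (either through claims or EMR"). Protocol 6.5.1.2 has the same sentence. No rule says which source takes precedence when both exist.

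**Who may be a control.** The sections disagree.
- SAP 4.4.2 says that, if applicable, "non-UHC members or UHC members who did not seek care at OptumCare facilities may be used as members of the control population".
- SAP 5.8.1.2 adds a separate exact-matching step for non-UHC participants, drawing on the controls left over.
- SAP 4.2, Table 1, uses EMR "for demographic characteristics, existing comorbidities, COVID test status and COVID hospitalization of potential non-UHC controls", and lists UHC claims as the comorbidity source for UHC controls.
- SAP 5.1.1 says: "Note that all populations for analyses are UHC members, and the following proposed analytical methods are for UHC members".
- SAP 5.8.2 limits propensity and double-score matching to UHC members.

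**Checks.** Balance is judged by standardized differences and variance ratios (Tables A8 and A8.2). SAP 5.8.3 treats any measurement error as random and negligible.

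**The concern.** Matching balances what is recorded, not what is true. If conditions are captured less completely in EMR than in claims, a control recorded as free of a condition is more likely to have it than the participant with the same record. Matched controls would then be truly sicker and the drug would look better. If EMR is the more complete source, the drug would look worse.

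No planned analysis would reveal this:
- Tables A8 and A8.2 compare recorded flags, which will look balanced.
- Double-score matching (SAP 5.8.2) reuses the same recorded covariates.
- The E-value and the proportion of unmeasured confounding are optional. They say how strong confounding would have to be, not whether the sources differ.
- The dismissal in SAP 5.8.3 fails here, because error that depends on the data source, and through it on the group, is not random with respect to treatment.

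Unlike sampling error, such a bias does not shrink as the study grows.

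**Working it through.** The plan states no figure for this problem, so there is none to reproduce. The calculation below shows the possible size.

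**Inputs.** All are assumptions, because the documents give none of them: true prevalence π = 0.30 in both source groups; risk ratio for hospitalization R = 2; specificity 1; sensitivity 0.80 in claims and 0.60 or 0.90 in EMR; no drug effect; exact match on the recorded flag.

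**Step 1: undetected disease among flag-negatives**, r = π(1 − se)/(1 − π·se).
- Claims, 0.80: 0.06/0.76 = 0.079
- EMR, 0.60: 0.12/0.82 = 0.146
- EMR, 0.90: 0.03/0.73 = 0.041

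**Step 2: mean risk in each matched group**, relative to a patient without the condition: f·R + (1 − f)[1 + r(R − 1)]. Here f = 0.30 × 0.80 = 0.24 is the flagged share, equal in both groups after matching.
- Participants (claims): 0.48 + 0.76 × 1.079 = 1.300
- Controls, EMR at 0.60: 0.48 + 0.76 × 1.146 = 1.351
- Controls, EMR at 0.90: 0.48 + 0.76 × 1.041 = 1.271

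**Step 3: spurious risk ratio**, participants over controls. Three independent, identical conditions cube the single-condition ratio.

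| Controls | One condition | Three conditions |
|---|---|---|
| All EMR-sourced, sensitivity 0.60 | 1.300/1.351 = 0.96 | 0.89 |
| 25% EMR-sourced, sensitivity 0.60 | 1.300/(0.75 × 1.300 + 0.25 × 1.351) = 0.99 | 0.97 |
| All EMR-sourced, sensitivity 0.90 | 1.300/1.271 = 1.02 | 1.07 |
| Same source as participants | 1.00 | 1.00 |

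A milder case (prevalence 20%, risk ratio 1.5, EMR sensitivity 0.60, all controls EMR-sourced) gives 0.98 and 0.95.

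**Wider range, one condition.** Take prevalence 30–50%, risk ratio 2–3 and participants' hospitalization risk 15%, the control rate assumed in SAP 4.4.2. The chances below are for a falsely significant benefit at 1,000 per group, by an unpaired two-proportion approximation rather than McNemar's test. The nominal chance in that direction is 2.5%.
- Claims 0.85, EMR 0.50, all controls EMR-sourced: control risk 16.0–16.8%, spurious ratio 0.94–0.90, chance 9–19%.
- The same with 25% EMR-sourced: ratio 0.98–0.97, chance about 4–5%.
- Claims 0.70, EMR 0.85, all EMR-sourced: ratio 1.03–1.07, against the drug.

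For comparison, the effect assumed in SAP 4.4.2 is 15% to 10%, a ratio of 10/15 = 0.67.

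**The case against.** The strongest reply is that the rest of the SAP already closes the gap. Section 5.1.1 restricts the analysis to UHC members. Table 1 ties EMR comorbidities to non-UHC controls. Section 4.4.2 plans UHC controls with continuous enrollment and access to claims. All three risk-factor iterations in 5.8.1.1 use UHC claims. On that reading every analysed control has claims covariates and the spurious ratio is about 1.00. This is a fair reading and may be what was intended. But the operative matching paragraph in 5.8.1.2 and the rows in 4.7 say otherwise, and an analyst could follow either.

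Second, common definitions partly exist: 2019 for comorbidities, six months before diagnosis for immunosuppressants, and one condition crosswalk and one drug list in Appendix 1. That stands. A common code list does not, however, make two sources equally complete, and Appendix 1 describes the immunosuppressant list as applied to claims only.

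Third, undetected disease is a form of residual confounding, which the E-value would partly address if it is run. That also stands, but it does not locate the problem or remove it.

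A reader might go further and infer that the match is biased, or biased in the drug's favour. The documents do not support this. Bias needs a difference in completeness and a material share of EMR-sourced controls. The documents give neither, and the direction depends on which source is more complete.

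**Conclusion.** The SAP permits group-dependent covariate sources, is inconsistent on whether controls with EMR-only history enter the primary match, and plans no check that would expose the consequence. The bias is possible, not demonstrated, and could go either way.

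Under the main assumptions the spurious ratio runs from 0.89 (three conditions, EMR less complete) to 1.07 (three conditions, EMR more complete), and both ends require every control to be EMR-sourced. At a 25% share the lower end is about 0.97. The three-condition figures also assume independent conditions with equal prevalence, risk ratio and sensitivity. All of these are smaller than the effect the SAP assumes. So the point should be settled before matching, but it would not by itself explain away an effect of that size.

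**What to change.** 1. For the primary propensity-matched analysis of UHC members, derive the comorbidity and immunosuppressant covariates, for matching and for adjustment, from UHC claims in both groups. Use the look-back in SAP 4.7 and the code lists in Appendix 1.
2. Delete the EMR alternative in SAP 4.7 and 5.8.1.2 for these covariates only, and align Protocol 6.5.1.2. Keep EMR for control symptoms, COVID test status, prior bamlanivimab and hospitalizations, where SAP 4.2, 4.7 and 5.8.1.3 rely on it. Stripping EMR back to symptom confirmation would remove eligibility and outcome data.
3. Reconcile SAP 4.2, 4.4.2, 4.7, 5.1.1 and 5.8.1.2 so that controls with EMR-only history, and the non-UHC exact-matching step, appear only in a sensitivity analysis.
4. Where controls have both sources, compare their claims and EMR flags. This replaces the assumption in SAP 5.8.3 with evidence.

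The cost is SAP and protocol wording, one cross-tabulation, and the loss of any non-UHC or EMR-only controls from the primary match. Section 5.1.1 already implies the non-UHC part of that loss. The change should be made before matching, while the choice cannot be influenced by results.

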5.3 Multiple Comparisons/Multiplicity

All analyses will be conducted at the two-sided 0.05 significance level without adjustments for multiplicity.

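### Standardized differences and variance ratios are planned without acceptance limits, so the decision to repeat matching rests on significance tests whose strictness changes with sample size

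*SAP*

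**What the plan says.** SAP 5.8.1.2 sets out three kinds of balance check after propensity score matching.

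- Standardized difference: "We will evaluate balance in covariates between study participants and matched controls by absolute standardized difference in mean".
- Variance ratio, with a reason for the choice: "variance ratio of propensity score and covariates since it is more robust in terms of sample size and covariate distribution requirements".
- Significance tests: "We will also conduct a hypothesis test to examine if a significant difference in matching covariates exists between treatment and control groups". The SAP names the Wilcoxon rank-sum test or t-test for continuous covariates and the chi-squared test for categorical ones. Protocol 6.5.1.2 names the first two and leaves room for other bivariate tests.

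The next sentence is the decision rule, and both documents have it: "We will use these tests to evaluate covariate balances before and after matching and repeat the processes if covariate imbalances remain".

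Neither document gives a limit for the standardized difference, a range for the variance ratio, or a significance level specific to balance tests. Optimal matching is held in reserve in case imbalance persists, and persistence is not defined either. Mock Tables A8 and A8.2 report standardized differences and variance ratios before and after matching, with no threshold. Mock Table A4 and its matched-population repeat, A4.2, carry a p-value column.

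The only general level is in SAP 5.3: "All analyses will be conducted at the two-sided 0.05 significance level without adjustments for multiplicity".

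On size, SAP 4.4.2 says that "the targeted number of study participants who are COVID-19 positive and consent to receive Bamlanivimab (LY3819253) is 7,500" and "we set the case:control ratio at 1:1 and plan to identify 7,500 matched controls". It then warns that "we may not achieve the target number of study participants, 7,500", and offers 1,000 participants with 1,000 matched controls as sufficient.

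**The concern.** Covariate balance describes the matched sample in hand. A p-value mixes the size of the difference with the number of pairs, so one observed difference can be acceptable in one sample and unacceptable in another. The SAP recognises this when it prefers the first two diagnostics for their robustness to sample size. It then attaches the accept-or-repeat decision to the diagnostic that depends on sample size most.

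This matters because there is no randomized comparator. The efficacy comparison depends on the match, and the first analysis listed for the Day 28 endpoint in SAP 5.8.1.3 is an unadjusted McNemar test. A trigger that is too strict leads to repeated re-matching over negligible differences, with no stated stopping point. A trigger that is too lax accepts a match with measured imbalance.

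**Working it through.** The plan states no figure for its balance rule, so there is none to reproduce. The check asks what limit on the standardized difference the rule implies.

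**Inputs**
- Level: two-sided 0.05, from SAP 5.3. That it applies to balance tests is an assumption, since no other level is given.
- Pairs: 7,500 (target) and 1,000 (fallback), from SAP 4.4.2. The values 500, 300 and 200 are illustrative assumptions.
- Benchmark: 0.10 as the standardized-difference limit. This is a convention and is not in the documents.

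**Step 1: implied limit.** For two groups of n with a common standard deviation, an observed standardized difference d gives z = d × √(n/2). It reaches p = 0.05 when d = 1.96 × √(2/n).

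| Pairs (n) | √(2/n) | Smallest d with p ≤ 0.05 |
|---|---|---|
| 7,500 | 0.0163 | 0.032 |
| 1,000 | 0.0447 | 0.088 |
| 500 | 0.0632 | 0.124 |
| 300 | 0.0816 | 0.160 |
| 200 | 0.1000 | 0.196 |

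**Step 2: where the test equals a 0.10 limit.** n = 2 × (1.96/0.10)² = 768, or about 770 pairs. Above that the test is stricter than 0.10; below it, more lenient.

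**Step 3: the same limits for a comorbidity flag.** Take a condition present in 25% of one group, where √(0.25 × 0.75) = 0.433. At 7,500 pairs the limit is about 0.032 × 0.433 = 0.014, so 25.0% against 26.4% is enough to trigger re-matching. For comparison, 25% against 29.5% is a standardized difference of 0.10, and 25% against 34% is 0.20.

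**Step 4: how often the test fires.** For an underlying difference δ, the probability is Φ(δ√(n/2) − 1.96) + Φ(−δ√(n/2) − 1.96).

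| δ | Pairs | δ√(n/2) | Probability flagged | Simulated (2,000 t-tests) |
|---|---|---|---|---|
| 0.05 | 7,500 | 3.06 | 0.865 | 0.862 |
| 0.10 | 1,000 | 2.24 | 0.609 | 0.595 |
| 0.20 | 200 | 2.00 | 0.516 | 0.511 |

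**Step 5: could the matched sample fall below 770 pairs?** SAP 4.4.2 drops participants for whom no control is found. SAP 5.1.1 confines the analysis populations to UHC members, and the propensity matching in SAP 5.8.1.2 covers UHC members only. Starting from 1,000 participants, the crossing point is reached if more than 1,000 − 768 = 232 of them (23%) are not propensity-matched. The documents give no match rate, so this is a condition and not a forecast.

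**The case against.** The strongest reply is that the plan already uses the right diagnostics. Standardized differences and variance ratios come first, for the right reason, and they fill the dedicated balance tables. The reference to tests in the re-matching sentence could loosely cover all three diagnostics. This part stands: it would be wrong to say that the plan judges balance by significance tests alone. It does not supply the missing rule, because two of the three diagnostics have no limit on any reading. Only the tests come with an implied cut-off.

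Second, at both documented sizes the implied limit (0.032 and 0.088) is tighter than 0.10, so the tests would flag every difference that a 0.10 rule flags. This also stands. A reader might infer that the SAP expects a matched sample far below 7,500 and that confounded matches will therefore pass. The text says only that the target may not be reached, and its alternative figure is 1,000 per group. At the 7,500 end the demonstrated consequence is needless re-matching; no bias has been shown.

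Third, a reader might infer that tightening the caliper would make the tests pass without improving balance. That does not follow. A tighter caliper brings paired propensity scores closer and generally improves balance. It also reduces n, and a p-value cannot separate the two effects.

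Fourth, SAP 5.2 and 5.8.1.3 plan covariate-adjusted models, and SAP 5.8.1.2 and 5.8.2 add subclassification with trimming and double score matching. These soften the effect of residual measured imbalance. They do not say when a match is acceptable.

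**Conclusion.** The point holds as a defect in the decision rule. The standardized difference and variance ratio have no acceptance limits, and the trigger for repeating the match most naturally refers to significance tests. That conflicts with the SAP's own preference for diagnostics robust to sample size.

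The implied limit varies about sixfold (0.196/0.032) between 200 and 7,500 pairs. At the target it is roughly a third of 0.10 and would force re-matching over negligible differences. At 1,000 pairs it is slightly stricter than 0.10 and does little harm. It becomes too lenient only below about 770 pairs, which is conditional on matching losses that the documents do not quantify.

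The conclusion assumes that the 0.05 level applies to balance tests, that the two-group normal approximation is adequate, and that 0.10 is a reasonable benchmark.

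**What to change.** In SAP 5.8.1.2, replace the re-matching sentence with a fixed criterion. Accept the match when every matching covariate and the propensity score have an absolute standardized difference below a stated limit (for example 0.10) and a variance ratio within a stated range (for example 0.5 to 2); otherwise re-specify and repeat. Let the same criterion define the persistent imbalance that leads to optimal matching. These values are conventions, so the study team should confirm them before matching starts.

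State that p-values for covariate differences, including those in Table A4.2, are descriptive and play no part in accepting a match. Require any covariate still above the limit to enter the adjusted outcome model. Make the same change in protocol 6.5.1.2.

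The cost is wording in two documents. No new data or output is needed, because Tables A8 and A8.2 already report both statistics before and after matching.
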